## 5.6. Handling of Missing Data

### 5.6.1. Efficacy Missing Data Rules:

Data summaries and analyses will use observed data only without imputation of missing values. Supplementary analysis will be performed to investigate the impact of data imputation on the primary endpoint as follows:

- 1) by assuming that subjects with missing data are treatment successes (“best case”) and
- 2) by assuming that subjects in the vehicle group with missing data are “treatment success” and that subjects in the TMB-001 groups with missing data are treatment failures (“worst case”) and
- 3) by assuming that subjects with missing data maintain their last observed rating from which treatment success or failure will be derived at Visit 6 (“LOCF”) and
- 4) by assuming that subjects with missing data are treatment failures (“non-responder”)

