## 6. ANALYSIS POPULATIONS

### 6.1. Intent-to-Treat (ITT) Population

All randomized subjects who received at least one dose of study medication will be included in the ITT population. Subjects will be analysed according to the treatment they are planned to receive according to the randomization schedule. The ITT population will be used for the analysis and presentation of all efficacy data.

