## 9.2. Efficacy Analysis

Efficacy analyses will be performed on both the ITT and PP populations with the ITT population considered primary.

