### 14.2 Efficacy Data Summaries

Table 14.2.1.1.1	Visual Index for Ichthyosis Severity – Change From Baseline (ITT)
Table 14.2.1.1.2	Visual Index for Ichthyosis Severity – Change From Baseline (PP)
Table 14.2.1.2.1	Visual Index for Ichthyosis Severity – Shift Table (ITT)
Table 14.2.1.2.2	Visual Index for Ichthyosis Severity – Shift Table (PP)
Table 14.2.1.3.1	Visual Index for Ichthyosis Severity – Success Rate (ITT)
Figure 14.2.1.3.1	Visual Index for Ichthyosis Severity – Success Rate (ITT)
Table 14.2.1.3.2	Visual Index for Ichthyosis Severity – Success Rate (PP)
Figure 14.2.1.3.2	Visual Index for Ichthyosis Severity – Success Rate (PP)
Table 14.2.1.4.1	Visual Index for Ichthyosis Severity – Success Rate – CMH analysis at Visit 6 (EOS) (ITT)
Table 14.2.1.4.2	Visual Index for Ichthyosis Severity – Success Rate – CMH analysis at Visit 6 (EOS) (ITT) (Best Case Analysis)
Table 14.2.1.4.3	Visual Index for Ichthyosis Severity – Success Rate – CMH analysis at Visit 6 (EOS) (ITT) (Worst Case Analysis)
Table 14.2.1.4.4	Visual Index for Ichthyosis Severity – Success Rate – CMH analysis at Visit 6 (EOS) (ITT) (LOCF)
Table 14.2.1.4.5	Visual Index for Ichthyosis Severity – Success Rate – CMH analysis at Visit 6 (EOS) (ITT) (Non-Responder Analysis)
Table 14.2.1.4.6	Visual Index for Ichthyosis Severity – Success Rate – CMH analysis at Visit 6 (EOS) (PP)
Table 14.2.1.5.1	Changes from Baseline in VIIS score relative to Visit 4 and Visit 5 – MMRM analysis (ITT)
Table 14.2.1.5.2	Changes from Baseline in VIIS score relative to Visit 4 and Visit 5 – MMRM analysis (PP)

---

Table 14.2.1.6.1	Time to VIIS-50 - Kaplan-Meier Analysis (ITT)
Figure 14.2.1.6.1	Time to VIIS-50 - Kaplan-Meier Analysis (ITT)
Table 14.2.1.6.2	Time to VIIS-50 - Kaplan-Meier Analysis (PP)
Figure 14.2.1.6.2	Time to VIIS-50 - Kaplan-Meier Analysis (PP)
Table 14.2.1.7.1	Visual Index for Ichthyosis Severity – Success Rate by identical body part (ITT)
Table 14.2.1.7.2	Visual Index for Ichthyosis Severity – Success Rate by identical body part (PP)
Table 14.2.1.8.1	Visual Index for Ichthyosis Severity – Success Rate by genetic mutation (ITT)
Table 14.2.1.8.2	Visual Index for Ichthyosis Severity – Success Rate by genetic mutation (PP)
Table 14.2.1.9.1	Visual Index for Ichthyosis Severity – Success Rate by phenotype (ITT)
Table 14.2.1.9.2	Visual Index for Ichthyosis Severity – Success Rate by phenotype (PP)
Table 14.2.1.10.1	Visual Index for Ichthyosis Severity – Success Rate by drug/BSA ratio (ITT)

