Table 14.2.2.3.2	Investigator’s Global Assessment – Success Rate (PP)
Figure 14.2.2.3.2	Investigator’s Global Assessment – Success Rate (PP)
Table 14.2.2.4.1	Investigator’s Global Assessment – CMH analysis at Visit 6 (EOS) (ITT)
Table 14.2.2.4.2	Investigator’s Global Assessment – CMH analysis at Visit 6 (EOS) (PP)
Table 14.2.2.5.1	Investigator’s Global Assessment – Cleared/Almost Cleared (ITT)
Table 14.2.2.5.2	Investigator’s Global Assessment – Cleared/Almost Cleared (PP)
Table 14.2.2.6.1	Time to 2 point decrease from baseline in IGA - Kaplan-Meier Analysis (ITT)
Table 14.2.2.6.2	Time to 2 point decrease from baseline in IGA - Kaplan-Meier Analysis (PP)
Table 14.2.2.7.1	Investigator’s Global Assessment – Success Rate by genetic mutation (ITT)
Table 14.2.2.7.2	Investigator’s Global Assessment – Success Rate by genetic mutation (PP)
Table 14.2.2.8.1	Investigator’s Global Assessment – Success Rate by phenotype (ITT)
Table 14.2.2.8.2	Investigator’s Global Assessment – Success Rate by phenotype (PP)

Table 14.2.2.9.1	Investigator’s Global Assessment – Success Rate by drug/BSA ratio (ITT)
Table 14.2.2.9.2	Investigator’s Global Assessment – Success Rate by drug/BSA ratio (PP)
Table 14.2.2.10.1	Investigator’s Global Assessment – Success Rate by drug/BMI ratio (ITT)
Table 14.2.2.10.2	Investigator’s Global Assessment – Success Rate by drug/BMI ratio (PP)
Table 14.2.2.11.1	Investigator’s Global Assessment – Success Rate by drug/kg ratio (ITT)
Table 14.2.2.11.2	Investigator’s Global Assessment – Success Rate by drug/kg ratio (PP)
Figure 14.2.2.11.1	Investigator’s Global Assessment – Success Rate by drug/weight ratio (ITT)
Figure 14.2.2.11.2	Investigator’s Global Assessment – Success Rate by drug/weight ratio (PP)
Table 14.2.2.12.1	Investigator’s Global Assessment – Success Rate by OTC Steroid Cream Usage (ITT)
Table 14.2.2.12.2	Investigator’s Global Assessment – Success Rate by OTC Steroid Cream Usage (PP)
Table 14.2.2.13.1	Investigator’s Global Assessment – Success Rate by assessment medium (ITT)
Table 14.2.2.13.2	Investigator’s Global Assessment – Success Rate by assessment medium (PP)
Table 14.2.2.14.1	Investigator’s Global Assessment – Success Rate by Drug Interruption (ITT)
Table 14.2.2.14.2	Investigator’s Global Assessment – Success Rate by Drug Interruption (PP)
Table 14.2.2.15.1	Proportion of Subjects with VIIS and IGA Treatment Success (ITT)
Table 14.2.2.15.2	Proportion of Subjects with VIIS and IGA Treatment Success (PP)

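### Early-termination scores can enter the primary VIIS-50 test as Week 12 values, the best-case rule does not give an upper bound, and IGA success has no missing-data analysis

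*SAP*

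**What the plan says.** **Population.** SAP 6.1: "All randomized subjects who received at least one dose of study medication will be included in the ITT population". SAP 9.2 runs efficacy on ITT and PP, "with the ITT population considered primary".

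**Missing data.** SAP 5.6.1 and Protocol 9.4.4 both state that "Data summaries and analyses will use observed data only without imputation of missing values". SAP 5.6.1 adds supplementary analyses "to investigate the impact of data imputation on the primary endpoint":
- best case: missing counts as success in every arm;
- worst case: missing counts as success on vehicle and as failure on TMB-001;
- LOCF: "by assuming that subjects with missing data maintain their last observed rating";
- non-responder: "by assuming that subjects with missing data are treatment failures".

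The fourth is not in Protocol 9.4.4. SAP Appendix 2 lists an ITT table for each (14.2.1.4.2 to 14.2.1.4.5).

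**Early exit.** In the Schedule of Activities (Protocol 1.2), a footnote to the Week 12/EOS column extends it to early termination. Protocol 8.1.4 has subjects who leave early complete the EOS procedures at their last or early-termination visit. SAP 9.1.1 flags success at Visit 6, with EOS in parentheses as the alternative. Protocol 9.4 leaves the accounting for missing data to the SAP. The SAP has no visit window for efficacy and no rule for classifying an exit score.

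**Key secondary endpoint.** For IGA success at Visit 6, Appendix 2 lists one ITT and one PP CMH table (14.2.2.4.1 and 14.2.2.4.2).

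**The concern.** Two programmers could follow this text and produce different primary results. One would treat a Week 5 exit score as the EOS value. The other would treat that subject as missing at Week 12. On the first reading, an analysis described as observed data only is partly a last-observation analysis, which the SAP lists only as supplementary. Those subjects are then not missing, so none of the four supplementary analyses tests their effect.

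The same reading matters in two other places. The third PP criterion (SAP 6.2) requires a VIIS measurement at Visit 6 (EOS), although the compliance criterion may exclude some early leavers anyway. Time to VIIS-50 (SAP 9.2.2) normally requires success to be maintained at the next observation but waives this when success is first reached at Visit 6 (EOS). An exit success labelled EOS would skip confirmation.

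Two smaller gaps sit beside this. Best case credits vehicle as well as TMB-001, so it is not the most favourable result for TMB-001. The key secondary endpoint faces the same missing visits as VIIS-50 but has no supplementary analysis.

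The trial is meant to supply initial VIIS response data and help choose a Phase 3 dose (SAP 4.5), so readers need to know what the reported rate describes.

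**Working it through.** **The plan's own figure.** 3 arms x 15 = 45, as stated. The documents give no power calculation, response rate or dropout rate, so there is nothing further to reproduce. All counts below are assumptions, for one active arm against vehicle, unstratified (the planned test is stratified by subtype).

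**Step 1: what the texts allow.** The column footnote, the instruction to complete EOS procedures at exit, and the SAP's EOS alternative all allow an exit score to be the EOS score. Against that, Protocol 8.1.4 dates the EOS visit to Week 12, Day 85, and speaks of leaving before Visit 6 (EOS), which separates the exit from that visit. Neither document settles it.

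**Step 2: effect on the headline.** Assume completers 6/12 active and 2/14 vehicle. Three active subjects and one vehicle subject leave early with a score. The vehicle exit score is a failure, and *s* of the three active exit scores are successes.

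- Exit scores excluded: 6/12 - 2/14 = 50.0% - 14.3% = **35.7 points**.
- Exit scores counted: (6 + s)/15 - 2/15.

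| s | Difference (points) | Shift from 35.7 |
|---|---|---|
| 0 | 26.7 | -9.0 |
| 1 | 33.3 | -2.4 |
| 2 | 40.0 | +4.3 |
| 3 | 46.7 | +11.0 |

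With exit scores counted, nobody in this example is missing, so all four supplementary analyses simply repeat the headline.

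**Step 3: the bracket.** Same data, exit scores treated as missing:

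- Worst case: 6/15 - 3/15 = 20.0
- Non-responder: 6/15 - 2/15 = 26.7
- Best case as written: 9/15 - 3/15 = 40.0
- Upper bound (TMB-001 missing = success, vehicle missing = failure): 9/15 - 2/15 = 46.7

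The planned pair spans 20.0 to 40.0, while the full range is 20.0 to 46.7. The gap is the one missing vehicle subject, 1/15 = 6.7 points.

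**Step 4: scale.** With true rates assumed at 40% and 15% and 15 per arm, the 95% half-width is 1.96 x sqrt(0.40 x 0.60/15 + 0.15 x 0.85/15) = 30.7 points.

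**Step 5: observed-case or non-responder as the headline?** Let *t* be the true rate, *d* the fraction missing, and *r* the dropout success rate as a fraction of the completer rate, the same in both arms. The completer rate is p = t/(1 - d + r x d). Bias in the difference:

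- observed-case: (1 - r) x (pA x dA - pV x dV)
- missing = failure: -r x (pA x dA - pV x dV)

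At 40% against 15%, with 1, 2 or 3 active and 1 vehicle missing:

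| r | Observed-case | Missing = failure |
|---|---|---|
| 0 | +1.8, +5.1, +8.9 | 0 |
| 0.5 | +0.9, +2.3, +3.9 | -0.9, -2.3, -3.9 |
| 1 | 0 | -1.7, -4.3, -7.0 |

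Neither method is less biased in general. With 1 active and 3 or 4 vehicle missing the signs reverse: observed-case gives -0.9 or -2.6 at r = 0, and missing = failure gives +0.3 or +1.3 at r = 1.

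**The case against.** **The text already points one way.** The column footnote and the SAP's EOS alternative suggest that an exit score is the EOS score, which would make this only a clarification. That is a fair reading, and it is why the point is minor. But Protocol 8.1.4 also separates the exit from Visit 6, and on the suggested reading the headline becomes partly LOCF without saying so.

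**Observed-case analysis is openly stated, and the non-responder table exists.** This stands. A reader might infer that the plan lacks sensitivity analyses, that the observed-case headline favours TMB-001, or that the non-responder analysis must replace it. The documents support none of these. Four supplementary ITT tables are planned for VIIS-50. The direction of bias depends on dropout behaviour that the documents do not give, and step 5 shows that the two methods can err in opposite directions.

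**Dropped denominators and counted exit scores are alternatives.** This also stands. A subject whose exit score is counted is not lost from the denominator, so the two effects cannot be added for the same subject. Observed-case exclusion would then apply only to subjects with no exit score, such as those lost to follow-up (Protocol 7.6). Subjects who stop treatment but attend Week 12 are affected by neither.

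**The plan never says that best and worst case bracket the effect.** True, but the names invite that use, and correcting the rule changes one line.

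**IGA has other analyses.** It has a PP test and an exploratory Kaplan-Meier analysis. Neither examines missing data in the Visit 6 proportion.

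**Conclusion.** The point holds and is minor. An early-termination score can enter the primary VIIS-50 test as a Week 12 value and so pass untouched through every supplementary analysis. It can also affect the third PP criterion and the confirmation rule for time to VIIS-50. In the assumed example the unwritten rule moves the headline by -9.0 to +11.0 points. Best case as written stops 6.7 points short of the upper bound. IGA success has no missing-data analysis.

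These sizes rest on invented counts in one unstratified comparison, and all are below the sampling error of about 31 points. The number of early exits, their timing and their scores are unknown. A reader might go further and infer an inflated type I error. The plan sets no alpha or decision rule and the study is not powered, so the documents do not support that.

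**What to change.** 1. **Exit scores.** State in SAP 5.6.1 and 9.1.1 that an early-termination score outside the Visit 6 window is not a Visit 6 value and is used only under LOCF. Refer SAP 6.2 and 9.2.2 to the same definition. The Schedule of Activities prints both plus or minus 7 and plus or minus 3 days for Visit 6, while Protocol 8.1.4 gives 7. These must be reconciled, though the difference matters only for exits 4 to 7 days from Day 85.
2. **Best case.** Define it as TMB-001 missing = success and vehicle missing = failure.
3. **IGA.** Run the same four supplementary analyses for IGA success at Visit 6.
4. **Reporting.** Show the analysed denominator in each ITT table and place the planned non-responder result (Table 14.2.1.4.5) beside the observed-case result. The primary analysis need not change.
5. **Record.** List these changes in SAP section 11, together with the non-responder analysis already added. That section now says there are none.

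**Cost.** Some protocol and SAP wording and four more IGA tables, mirroring 14.2.1.4.2 to 14.2.1.4.5. The main drawback is that off-window exit scores leave the observed-case analysis and count as failures in the non-responder table, even if VIIS-50 was met at exit. In the example the non-responder difference is 26.7 points even when all three active exits were successes. The LOCF table would show 46.7 in that case, so the effect stays visible.

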9.4.4 Missing Data

Data summaries and analyses will use observed data only without imputation of missing values. Supplementary analysis will be performed to investigate the impact of data imputation on the primary endpoint as follows:

1. By assuming that subjects with missing data are treatment successes (“best case”); and
2. By assuming that subjects in the Vehicle group with missing data are “treatment success” and that subjects in the TMB-001 groups with missing data are treatment failures (“worst case”).
3. By assuming that subjects with missing data maintain their last observed rating from which treatment success or failure will be derived at Visit 6 (“LOCF”).

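### The best-case rule for missing VIIS-50 also counts missing vehicle subjects as successes, so it is not the most favourable TMB-001 versus vehicle difference and can fall below the observed one

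*SAP*

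**What the plan says.** The main analyses are observed-case: "Data summaries and analyses will use observed data only without imputation of missing values" (SAP 5.6.1; Protocol 9.4.4 agrees). The SAP then adds sensitivity analyses, with their scope stated: "Supplementary analysis will be performed to investigate the impact of data imputation on the primary endpoint as follows". There are four rules:

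- Rule 1, labelled best case: "by assuming that subjects with missing data are treatment successes". Protocol 9.4.4 has the same rule, again with no arm named: "By assuming that subjects with missing data are treatment successes".
- Rule 2, labelled worst case: vehicle subjects with missing data are successes, "and that subjects in the TMB-001 groups with missing data are treatment failures".
- Rule 3: LOCF.
- Rule 4: non-responder, every missing subject a failure. This rule is in the SAP only.

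SAP Appendix 2 gives each rule its own ITT CMH table for VIIS-50 (Tables 14.2.1.4.2 to 14.2.1.4.5). For the key secondary endpoint, IGA success, it lists one ITT CMH table and one PP table (14.2.2.4.1 and 14.2.2.4.2), with no imputed versions. SAP section 11 reports no changes from the protocol's analysis.

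**The concern.** The endpoint is compared between arms, and two adjacent tables are labelled best case and worst case. A reader will naturally take the pair as the range that missing data could produce for the TMB-001 versus vehicle difference. Rule 2 does give the lower end of that range. Rule 1 does not give the upper end, because it credits the vehicle arm as well as the active arm. The shortfall comes from the vehicle arm, so it is the same for both concentrations.

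At stake is how the sensitivity results are read. SAP 4.5 says that these data will support sample-size calculations for later studies and dose selection for Phase 3. An observed difference that lies outside its own best/worst pair would be confusing in that setting.

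**Working it through.** **Inputs.** From SAP 4.5: 15 per arm. From SAP 5.6.1: the four rules. The documents give no response or loss rates, so every count and rate below is an assumption. There is no stated figure to reproduce beyond 3 × 15 = 45. Differences are crude, in percentage points, and ignore the CI-subtype strata.

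**Formulas.** Let a and v be observed successes, and ma and mv the numbers missing, in a TMB-001 arm and in vehicle.

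- Observed = a/(15 − ma) − v/(15 − mv)
- Rule 1 = (a + ma − v − mv)/15
- Rule 2 = (a − v − mv)/15
- Rule 4 = (a − v)/15
- Most favourable = (a + ma − v)/15

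**Algebra.**

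- Most favourable minus rule 1 = mv/15, which is 6.7, 13.3 and 20.0 points for 1, 2 and 3 missing vehicle subjects, and zero if none is missing.
- With an equal missing fraction m in both arms, rule 1 = (1 − m) × observed. It is therefore below any positive observed difference. With equal arm sizes it also equals rule 4, since ma = mv cancels.
- Most favourable is never below observed, because (a + ma)/15 ≥ a/(15 − ma) and v/15 ≤ v/(15 − mv). By the same argument rule 2 is never above observed. The observed result can therefore leave the planned pair only at the top.

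**Examples (assumed counts).**

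| TMB-001 v vehicle, observed | Missing | Observed | Rule 2 | Rule 1 | Rule 4 | Most favourable |
|---|---|---|---|---|---|---|
| 8/13 v 5/13 | 2, 2 | +23.1 | +6.7 | +20.0 | +20.0 | +33.3 |
| 8/14 v 5/12 | 1, 3 | +15.5 | 0.0 | +6.7 | +20.0 | +26.7 |
| 5/11 v 2/14 | 4, 1 | +31.2 | +13.3 | +40.0 | +20.0 | +46.7 |

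In the first two rows the observed difference lies above the planned best case. In the second, so does the non-responder result. In the third, where more active subjects are missing, rule 1 does exceed the observed difference, though it is still 6.7 points short of the most favourable case.

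**Frequency.** Exact binomial enumeration over ma, mv, a and v, with loss independent of outcome:

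| Success, TMB-001 v vehicle | Loss, TMB-001 v vehicle | Rule 1 below observed |
|---|---|---|
| 60% v 35% | 5% v 5% | 47% |
| 60% v 35% | 10% v 10% | 62% |
| 60% v 35% | 20% v 20% | 70% |
| 60% v 35% | 10% v 20% | 87% |
| 60% v 35% | 20% v 10% | 41% |
| 35% v 35% | 10% v 10% | 46% |

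Under the most favourable definition the share is 0% in every row.

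**Size of the gap.** With equal loss m, the mean of observed minus rule 1 is m × (60 − 35) points: about 1.2, 2.5 and 5.0 at 5%, 10% and 20%. Among trials where rule 1 is below observed, the median gap is 4.3, 5.1 and 8.1 points. For scale, a crude 95% interval at 15 per arm has half-width 1.96 × √(0.60 × 0.40/15 + 0.35 × 0.65/15) ≈ 35 points.

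**The case against.** The strongest reply is that this is a label on a supplementary table. For one arm's response rate, setting all missing subjects to success is the best case, and rules 1 and 4 bound each arm exactly. The most favourable difference can also be assembled from planned output: take TMB-001 from Table 14.2.1.4.2 and vehicle from Table 14.2.1.4.5. In the first example that is 10/15 − 5/15 = +33.3. Only its CMH test and confidence interval are absent. The bound that guards against a false positive claim is rule 2, and it is right. The typical gap is small beside the sampling error.

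All of that stands, and it limits the size of the point. It does not rescue the label, because the table is a CMH comparison between arms and sits next to a worst case defined by arm.

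A reader might go further in three ways that the documents do not support.

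- *IGA success lacks a required sensitivity analysis.* Limiting imputation to the primary endpoint is stated openly and matches the protocol. IGA versions would be useful, but their absence is not an error. Missing scores by arm are largely recoverable from the planned disposition table, listings and denominators.
- *Nothing says how an early-termination score is treated.* Footnote b of the Schedule of Activities and Protocol 8.1.4 place early-termination assessments with Visit 6, and SAP 9.1.1 refers to Visit 6 or EOS. These suggest that such scores count. What is missing is an explicit analysis sentence.
- *Early scores should be set to missing.* That could make the primary result less conservative. Suppose 8/11 v 5/14, with 4 active and 1 vehicle leavers who all fail at an early-termination visit. Counting those scores gives 8/15 − 5/15 = +20.0. Treating them as missing gives +37.0, because the failures leave the denominator.

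**Conclusion.** Rule 1 as written is not the most favourable TMB-001 versus vehicle contrast whenever a vehicle subject is missing. The shortfall is exactly the vehicle missing fraction, 6.7 points per subject at 15 per arm, whatever the response rates. It can fall below the observed difference, and always does when missing fractions are equal and the observed difference is positive. It need not do so when more active than vehicle subjects are missing.

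How often this happens rests on assumed rates, on loss unrelated to outcome and on ignoring strata. Under 60% v 35% with equal loss it is 47% to 70% of trials, with a mean gap of 1.2 to 5.0 points.

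The SAP does not claim that the pair brackets the result; the labels invite that reading. The observed-case primary analysis is disclosed and is not at fault here, and the lower bound is sound. The point is worth fixing because the correction is cheap, not because it threatens the primary result.

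**What to change.** 1. In SAP 5.6.1 define best case (Table 14.2.1.4.2) as TMB-001 missing = success and vehicle missing = failure. The best/worst pair then brackets each TMB-001 versus vehicle difference. Keep the present rule 1, if wanted, under a neutral name such as *all missing = success*.
2. Record this change in SAP section 11, together with rule 4, which the SAP already adds to the three rules in Protocol 9.4.4.
3. Minor and optional: add non-responder, best-case and worst-case tables for IGA success.
4. Also minor: state in one sentence whether an early-termination score is analysed as Visit 6, and apply the answer to VIIS-50, IGA success, PP criterion 3 (SAP 6.2) and the Visit 6 exception in time to VIIS-50 (SAP 9.2.2). No particular window is proposed, for the reason given under the objection.

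The cost is SAP wording, one re-run VIIS-50 table, a section 11 entry and, if taken up, a few IGA tables. It needs no new data and no change to trial conduct.
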